Other Clinical Endpoints	 Target lesion failure (TLF) at 30 days, 1, 2 and 3 years post-procedure, defined as a composite rate of cardiovascular death, target vessel myocardial infarction and clinically-driven target lesion revascularization (TLR). Target vessel failure (TVF) at 30 days, 180 days, and 1, 2 and 3 years post-procedure, defined as a composite rate of cardiovascular death, target vessel myocardial infarction, and target vessel revascularization (TVR). Clinically-driven target lesion revascularization (TLR) at 1, 2 and 3 years post-procedure. Clinically-driven target vessel revascularization (TVR) at 180 days and 1, 2 and 3 years post-procedure. Rate of vascular access site complication, defined as the combined rate of hematoma, AV fistula or a pseudoaneurysm that required intervention, such as surgical repair or transfusion, prolonged hospital stay or required a new hospital admission. Lesion success (per device), defined as achievement of a final in-lesion residual diameter stenosis of <30% (by QCA), using any device after wire 						

	passage through the lesion. Pre- and post-dilatation of the lesion with a
	non-study device is considered part of assigned device treatment.
	• Technical success (per device), defined as achievement of a final in-lesion residual diameter stenosis of <30% (by QCA), using the CVT Everolimus-coated PTCA Catheter without a device malfunction after wire passage through the lesion. Pre- and post-dilatation are considered part of assigned device treatment.
	• Clinical success (per subject) defined as technical success without the occurrence of major adverse cardiac events during the procedure.
	• Procedural success (per subject) defined as lesion success without the occurrence of major adverse cardiac events during the procedure.
Angiographic, IVUS	Angiographic endpoints (subset of 25 subjects):
and OCT Endpoints	• In-segment LLL at 180 days
	• In-stent and in-segment % diameter stenosis (%DS) at 180 days
	• In-stent and in-segment angiographic binary restenosis (ABR) rate at 180 days
	IVUS endpoint (subset of 15 subjects):
	• In-stent % volume obstruction (%VO) at 180 days
	OCT endpoints (subset of 10 subjects):
	• % of stent strut coverage at 180 days
Subject	Subjects with documented in-stent restenosis in native coronary arteries.
Population	
Treatment Strategy	• Treatment of a single in-stent restenosis coronary artery lesion with up to two (2) CVT Everolimus-coated PTCA Catheters.

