3.4 Other Clinical Endpoints

³ Garcia-Garcia HM, McFadden EP, Farb A, et al. Standardized End Point Definitions for Coronary Intervention Trials: The Academic Research Consortium-2 Consensus Document. Circulation. 2018;137(24):2635-2650. doi:10.1161/CIRCULATIONAHA.117.029289

⁴ Moussa ID, Klein LW, Shah B, et al. Consideration of a new definition of clinically relevant myocardial infarction after coronary revascularization: an expert consensus document from the Society for Cardiovascular Angiography and Interventions (SCAI). J Am Coll Cardiol. 2013;62(17):1563-1570. doi:10.1016/j.jacc.2013.08.720

- Target lesion failure (TLF) at 30 days, 1, 2 and 3 years, post-procedure, defined as a composite rate of cardiovascular death, target vessel myocardial infarction and clinically-driven target lesion revascularization (TLR).
- Target vessel failure (TVF) at 30 days, 180 days and 1, 2 and 3 years post-procedure, defined as a composite rate of cardiovascular death, target vessel myocardial infarction, and target vessel revascularization (TVR).
- Clinically-driven target lesion revascularization (TLR) at 1, 2 and 3 years post-procedure.
- Clinically-driven target vessel revascularization (TVR) at 180 days and 1, 2 and 3 years post-procedure.
- Rate of vascular access site complication, defined as the combined rate of hematoma, AV fistula or a pseudoaneurysm that required intervention, such as surgical repair or transfusion, prolonged hospital stay or required a new hospital admission.
- Lesion success (per device), defined as achievement of a final in-lesion residual diameter stenosis of <30% (by QCA), using any device after wire passage through the lesion. Pre- and post-dilatation of the lesion with a non-study device is considered part of assigned device treatment.
- Technical success (per device), defined as achievement of a final in-lesion residual diameter stenosis of <30% (by QCA), using the CVT Everolimus-coated PTCA Catheter without a device malfunction after wire passage through the lesion. Pre- and post-dilatation are considered part of assigned device treatment.
- Clinical success (per subject) defined as technical success without the occurrence of major adverse events during the procedure.
- Procedural success (per subject) defined as lesion success without the occurrence of major adverse events during the procedure.

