Record an image of the target lesion after pre-dilatation is completed. Ensure to perform an angiography distal to the target lesion. Assess the subject for any angiographic complications after pre-dilatation and confirm the lesion to be treated meets the study angiographic inclusion and exclusion criteria.

Successful pre-dilatation of the target lesion is defined as:

- Residual stenosis of <30% after pre-dilatation (per visual estimate) AND
- No major (>Grade B) flow-limiting dissection.

In case of unsuccessful pre-dilatation of the target lesion planned to be treated with the investigational device, the subject should be considered a screen failure and all lesions should be treated as per standard of care.

Treatment with CVT Everolimus-coated Catheter

It is recommended to select a CVT EVE-PTCA Catheter with a balloon length that allows for coverage of the targeted lesion plus approximately 2 mm additional coverage, by visual estimate, on each side of the lesion while not allowing the balloon length extend beyond the edges of the stent.

The balloon should be inflated for 60 seconds in order to allow for an optimal drug delivery to the surrounding tissue.

Post-Procedure Angiography Subset

A subset of twenty-five (25) subjects will complete post-procedure angiography assessment of the target vessel, as per the angiographic core laboratory guidelines, at 6 months post-procedure.

The 25 subjects undergoing angiographic follow up will represent the first subjects enrolled into the study, with no more than 15 patients undergoing angiographic follow up from a single site.

Note: The end of the procedure is defined as the time after a complete final angiogram has been performed and the last guidewire and catheter have been removed. In case the subject needs to return to the procedure room and a guiding catheter is reinserted for dilatation, this is considered a reintervention. Removal of the sheath(s) may be done at the Investigators discretion.

All catheters, including the CVT Everolimus-coated PTCA Catheter, should be delivered and deployed per their respective Instructions for Use (reference Appendix E for CVT Everolimus-coated PTCA Catheter IFU). All balloon inflations should be captured per the angiographic core laboratory guidelines.

Intravascular Ultrasound Examination (IVUS)

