Undetermined. It is defined as a death not attributable to any other category because of the absence of any relevant source documents. Such deaths will be classified as cardiovascular for end point determination.

Device Malfunction

A malfunction is a failure of a device to meet its performance specifications or otherwise perform as intended. Performance specifications include all claims made in the labeling of the device. The intended performance of a device refers to the intended use for which the device is labeled

Dissection Grades

National Heart, Lung, and Blood Institute (NHLBI) Dissection Classification System: (0, A, B, C, D, E, F)

- 0: No dissection
- A Minor radiolucent areas in the lumen without impairment of flow or persistent dye staining after contrast runoff
- B Luminal flap that is radiolucent and that runs parallel to the vessel wall with contrast injection but without impairment of flow or persistent dye staining after contrast runoff
- C: Contrast appears outside of the vessel lumen as an "extra-luminal cap". The staining appears even after contrast clears the lumen
- D: Spiral radiolucent luminal filling defects. Often persistent staining after contrast clears from the vessel.
- E: New and persistent filling defects in the vessel lumen.
- F: Lesions that progress to impaired flow or total occlusion.

Embolism

Formation of a thrombus within the target lesion with migration or atherosclerotic emboli migration to a distal artery.

Hematoma

A localized collection of blood in a space or tissue.

Intent-to-Treat (ITT) Population

The principle of including outcomes of all patients in the analysis who are enrolled into the clinical trial/investigation, regardless of the treatment actually received.

Late Lumen Loss (LLL)

Calculated as Minimum Lumen Diameter (MLD) post-procedure - MLD at follow-up

Mean in-lesion Late Loss will also be measured: (Mean In-lesion MLD, post-procedure) – (Mean In-lesion MLD at follow-up)

Lead Principal Investigator

A physician-specialist, related to the study, which is responsible for the overall conduct of the trial at all sites.

Major Adverse Cardiac Event (MACE)

Death, myocardial infarction (Q wave and non-Q wave), emergent coronary bypass surgery, or clinically driven repeat target lesion revascularization by percutaneous or surgical methods.

Minimum Lumen Diameter (MLD)

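### Clinical and procedural success stop counting events once the last catheter is out, so a major cardiac event that begins between then and discharge still leaves the subject a success

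*Combined protocol and SAP*

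**What the plan says.** Section 3.4 (Other Clinical Endpoints) defines two per-subject acute endpoints: "Clinical success (per subject) defined as technical success without the occurrence of major adverse events during the procedure" and "Procedural success (per subject) defined as lesion success without the occurrence of major adverse events during the procedure". The Protocol Summary has the same window but a different event term: "Clinical success (per subject) defined as technical success without the occurrence of major adverse cardiac events during the procedure".

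Section 4.3 says when the procedure is over. The end is "defined as the time after a complete final angiogram has been performed and the last guidewire and catheter have been removed", and "In case the subject needs to return to the procedure room and a guiding catheter is reinserted for dilatation, this is considered a reintervention". The note appears three times (angiography, IVUS and OCT) in general wording, and it is the only definition of the end of the procedure in the documents.

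Appendix B defines MACE as "Death, myocardial infarction (Q wave and non-Q wave), emergent coronary bypass surgery, or clinically driven repeat target lesion revascularization", by percutaneous or surgical methods. It does not define the broader term used in Section 3.4. For MI after revascularization, Appendix B relies on CK-MB or troponin rises within 48 hours of the procedure. Section 4.5 and Table 3 schedule one set of biomarkers after the procedure, before discharge, with no fixed hour. Section 6.4 makes all secondary endpoints descriptive.

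**The concern.** An acute success endpoint should separate subjects who leave hospital with a good result from those who do not. Here the event part of the definition closes at catheter removal. Suppose the vessel closes two hours later and the subject has a repeat PCI and a large MI before discharge. Read literally, that subject is both a clinical and a procedural success.

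At stake is what these two rates say about a first-in-human device. They are its only per-subject acute composites. With so short a window they add little to technical success and lesion success, and any misclassification favours the device.

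**Working it through.** The plan gives no expected rate, sample size or power for these endpoints, so there is no figure of its own to reproduce. The check is mainly one of definitions.

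**Which MACE components can fall inside the window**

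| Component (Appendix B) | Begins on the table | Begins after catheter removal, before discharge |
|---|---|---|
| Death | counts | does not count |
| MI | can count, if dated to the procedure | does not count |
| Emergent bypass | can count, if begun before catheter removal | does not count |
| Repeat TLR | bailout is part of the index session (Section 4.3) | does not count; return for dilatation is a reintervention |

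Nothing in the documents extends the window to 48 hours or to discharge. The adverse event log in Appendix L separates intra-operative from post-operative events, so a programmer would naturally map the window to the intra-operative box. The plan gives no rule for dating an MI that is first seen in the pre-discharge sample, and such an MI is likely to be logged as post-operative.

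**Direction and size**

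Input: N = 50 (Section 3.6).

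- Effect per affected subject who otherwise meets the definition: 1/50 = 2 percentage points, always upward.
- Appendix J, row 2d (thrombosis or persistent occlusion leading to MI) is the only row labelled solely as a post-procedure complication. Its rate is above 0.1% and below 1%.
- Expected subjects: 50 × 0.001 = 0.05 to 50 × 0.01 = 0.5.
- Expected overstatement: 0.05 × 2 = 0.1 point to 0.5 × 2 = 1 point.
- Chance of at least one such subject, 1 − (1 − p)^50: 4.9% at p = 0.1% and 39.5% at p = 1%.
- Sensitivity: adding the whole of row 3f (death, peri- or post-procedure, also below 1%) gives at most 50 × 0.02 = 1 subject, or 2 points.

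With the exact 95% intervals that Section 6.4 specifies, one affected subject turns a true 49/50 = 98% (89.4 to 99.9) into a reported 50/50 = 100% (92.9 to 100).

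These figures are illustrative. Row 2d is not limited to the period before discharge, and it does not cover repeat TLR without MI.

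**The case against.** The strongest reply is that the definitions turn on when an event occurs, not on when it is detected. An infarct caused by a dissection on the table happened during the procedure even if troponin is read the next day. Appendix B's abrupt-closure entry also links closure during the procedure to a resulting MI or death. This stands. A reader might infer that no peri-procedural MI can ever count and that only death on the table is left. The documents do not support that: MI, death or surgery that begins on the table can still make a subject a failure.

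A reader might also take Appendix J row 2c (above 1% and below 10%) and put the overstatement at 1 to 10 points. That is not a valid basis. Row 2c includes events at catheter deployment, which can count under the present wording. Its harm includes ischemia short of MI, while Appendix B sets a high biomarker threshold for MI.

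Third, most of these events are captured elsewhere. Target vessel MI, clinically driven TLR and cardiovascular death count in target lesion failure (TLF) at 30 days. Such events also enter the 6-month primary safety endpoint, whose death term in Section 3.2 is cardiac death. This stands too, and it limits the point to the two success rates. The cover is not complete. MACE includes any death and any MI, so an in-hospital MI outside the target vessel, or a non-cardiovascular death after catheter removal, would count in neither success rate and in neither TLF nor target vessel failure.

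Finally, the window is openly stated, and Section 10.7 leaves event criteria to the clinical events committee. But those criteria are to be based on the protocol, and the protocol's own text fixes the end of the procedure.

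**Conclusion.** The point holds in a limited form. MACE that begins after catheter removal and before discharge cannot make a subject a clinical or procedural failure, and an MI recognised only from the pre-discharge sample is likely to be missed. The bias is upward only, at 2 percentage points per affected subject. Its total cannot be derived from the documents; about 0.1 to 1 point follows if row 2d is taken as the rate of such events.

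A reader might go on to infer that the primary safety result or its power is compromised. It is not: both success rates are descriptive, with no hypothesis or decision rule attached. The mismatch in event terms between Section 3.4 and the Protocol Summary is a separate defect and needs reconciling in any case.

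**What to change.** In Section 3.4 and the Protocol Summary, for both endpoints, replace the procedure-only window with: *from the start of the index procedure through hospital discharge*. Use the defined term MACE in both places. State that MI is judged by the Appendix B criteria on the pre-discharge biomarkers and ECG.

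The cost is a change to four endpoint lines. The biomarkers, ECG and adverse events through discharge are already collected, and no visit, test or change in sample size is needed. There are two downsides. Reported success rates may be slightly lower. Because the pre-discharge draw has no fixed hour, MI ascertainment may not cover the full 48 hours in subjects discharged early. The case report form records the time of each enzyme test, so the report can show how much of that period was covered.

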3.5 Angio-IVUS-OCT Endpoints

Angiographic endpoints:

- In-segment LLL at 180 days
- In-stent and in-segment % diameter stenosis (%DS) at 180 days
- In-stent and in-segment angiographic binary restenosis (ABR) rate at 180 days

IVUS endpoint:

• In-stent % volume obstruction (%VO) at 180 days

OCT endpoints:

• % of stent strut coverage at 180 days

3.6 Study Population

Subjects included in this study will be comprised of male and female subjects derived from the general interventional cardiology population. This study will include fifty (50) subjects with a with a single in-stent stenotic lesion in a native coronary artery, eligible to be treated by interventional therapy and who meet all the inclusion criteria and none of

the exclusion criteria of this study.

3.7 Ethical Considerations

The trial will be conducted in accordance with this Clinical Investigational Plan (CIP), the Declaration of Helsinki, BS EN ISO 14155:2020 standards and Good Clinical Practices. The conduct of the trial will be approved by the appropriate Medical Ethics Committee (MEC) of the respective clinical site and as specified by local and country specific regulations.

3.8 Subject Inclusion Criteria

Study subjects must fulfill the following clinical criteria:

- 1. Subject must be at least 18 years of age.
- 2. Subject or his/her legally authorized representative provides written informed consent prior to any clinical investigation related procedure, as approved by the appropriate Ethics Committee of the respective clinical site
- 3. Subject must agree to undergo all clinical investigation plan-required follow-up visits, angiograms, IVUS/OCT and examinations.

Angiographic Inclusion Criteria

- 1. Target lesion must be located within a stent placed in a native epicardial coronary vessel with visually estimated nominal vessel diameter of \geq 2.0mm and \leq 3.5mm. The previously implanted stent can be bare metal or a drug eluting stent.
- 2. Target lesion must measure ≤ 24 mm in length by visual estimation.
- 3. The target lesion must be with a visually estimated stenosis of $\ge 0\%$ and <100% with a TIMI flow of ≥ 1 .
- 4. Non-clinical investigation, percutaneous intervention for lesions in a non-target vessel is allowed if done ≥90 days prior to or if planned to be done 6 months after the index procedure.
- 5. Non-clinical investigation, percutaneous intervention for lesions in the target vessel is allowed if planned to be done 6 months after the index procedure.

3.9 Subject Exclusion Criteria

Subjects with any of the following criteria should be excluded:

- 1. Subject with known diagnosis of acute myocardial infarction (AMI) within 30 days preceding the index procedure and CK-MB and troponin have not returned within normal limits at the time of procedure.
- 2. The subject is currently experiencing clinical symptoms consistent with AMI.
- 3. Subject has current unstable arrhythmia.
- 4. Subject has a known left ventricular ejection fraction (LVEF) <25%.
- 5. Subject has a known hypersensitivity or contraindication to aspirin, both heparin and bivalirudin, both clopidogrel and ticlopidine and structurally related compounds, everolimus or contrast sensitivity that cannot be adequately pre-medicated.

- 6. Subject has known renal insufficiency (e.g., serum creatinine level of more than 2.5 mg/dL, (i.e. 221 μmol/L) within 7 days prior to index procedure or subject on dialysis.
- 7. Subject has a history of bleeding diathesis or coagulopathy or will refuse blood transfusions.
- 8. Subject has had a cerebrovascular accident (CVA) or transient ischemic neurological attack (TIA) within the past six months.
- 9. Subject has other medical illness (e.g., cancer or congestive heart failure) or known history of substance abuse (alcohol, cocaine, heroin etc.) that may cause non-compliance with the clinical investigation plan, confound the data interpretation or is associated with a limited life expectancy (i.e., less than one year).
- 10. Subject is already participating in another clinical investigation that has not yet reached its primary endpoint.
- 11. Subject is not in the opinion of the investigator an acceptable candidate to participate in the study.
- 12. In stent lesions for stent are located within an arterial or saphenous vein graft.
- 13. The target vessel contains visible thrombus.
- 14. Pregnant or lactating females.

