4.1 Baseline Assessments

Subject preparation will occur in accordance with standard hospital policy for the care of interventional endovascular subjects. Baseline assessments will be documented in the subject medical record and on the case report form (CRF) as appropriate.

Subject History

Subject history will include but not be limited to the following risk factors and comorbidities: age, height, weight, body mass index (BMI), gender, hypertension, hyperlipidemia, diabetes mellitus, smoking, ischemic heart disease (history of myocardial infarction, angina pectoris, previous percutaneous or surgical coronary revascularization), history of peripheral vascular disease (previous percutaneous or surgical revascularization), deep vein thrombosis, congestive heart failure, renal insufficiency, renal disease, liver disease, cerebrovascular disease (known carotid artery disease, history of minor or major stroke or transient ischemic attack), and chronic obstructive pulmonary disease (COPD).

Medication History

A medication history should be documented which includes chronic concomitant medications and protocol required medications.

Clinical Assessments

A physical examination should be documented. The exam will include heart rate, blood pressure and body temperature.

Laboratory Assessments

A pregnancy test should be administered to all female subjects of childbearing potential within 14 days prior to the procedure.

The following laboratory tests should be obtained for all subjects within 7 days prior to the index procedure.

- Complete Blood Count
- Creatinine
- Absolute Platelet Count
- Coagulation tests as per standard of care of the hospital (e.g., Prothrombin Time (PT) and activated Prothrombin Time (aPTT).

The following laboratory tests should be obtained for all subjects within 72 hours of the index procedure.

- CK and/or CK-MB and cardiac troponin (cTn)
- 12 lead ECG.

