5. CONTRAINDICATIONS

5.1. Contraindications

Refer to the Clinical Investigational Plan for study exclusion criteria.

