8.3. Carcinogenicity, Genotoxicity and Reproductive Toxicology

No long-term studies have been performed to evaluate the carcinogenic potential of the CVT Everolimus-coated PTCA Catheter. Do not use the CVT Everolimus-coated PTCA Catheter in women who are pregnant or intending to become pregnant.

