# CVT ISR Trial FIH Trial Protocol Number: TP1125 Case Report Forms

Г

Site ID		Subject Number Birth Year						
Pre-Procedure Laboratory Blood Values								
1. Is the subject female and of childbearing potential? $\Box$ YES $\Box$ NO $\Box$ NA (if N								
	1.1.	If yes, sample date of pregnancy test:						
	1.2.	Result of pregnancy test: $\Box$ Postive $\Box$ Negative $\Box$ Not Done						

Blood Test Sample Date:	
DD MM YYYY	

_			Range		Clinically Significant		Comment	
Parameter	Result	Unit	IN	O High	UT Low	(if out o Yes	of range) No	or Not Done
WBC								□ Not Done
Differential WBC								
Eosinophils								□ Not Done
Basophils								□ Not Done
Neutrophils								□ Not Done
Monocytes								□ Not Done
Lymphocytes								□ Not Done
Hemoglobin								□ Not Done
Hematocrit								□ Not Done
Absolute Platelet Count								□ Not Done
Serum Creatinine								□ Not Done
Prothrombin Time								□ Not Done
Activated Prothrombin Time								□ Not Done
Site ID	Subject Number	Birth Year						
---------	----------------	------------						
---------	----------------	------------						

CK and/or CK-MB cardiac Troponin

 $\hfill\square$  Not done.

Cardiac Enzymes	Date of Test: (dd/mm/yyyy)	Time (24 hour clock)	Value (U/L)	Upper Normal Limit (U/L)
СК	//	:		
CK-MB	//	:		
Troponin	//	:		

Site	e ID Subjec	t Number	Birth Year
	Antiplatelet and A	Anticoagulant Me	dication
1. 2.	Was Aspirin Administered Was an Antiplatelet Administered	□ YES □ □ YES □	NO NO
3.	What anticoagulant was administered	:	
4.	Was a glycoprotein (GP) IIb/IIIa recep	ptor blocker used: 🗆 Y	YES $\Box$ NO

Site ID	Subject Number	Birth Year
Target Lesion Treatment D	Procedural Form CB # 1 □ DCB # 2 □	

 
What was the location         
 
□ Femoral □ F
 
 
 
Arterial sheath size □
 
	of vascular access Radial □ Brachial 5F □ 6F □ 7F □ 8F	

 
3. ISR Stent Location
 
Right Coronary Artery
 
Proximal      Mid      Distal
 
Right Post. Descending
 
	
 
□ Left Anterior Descending
 
□ Proximal □ Mid □ Distal
 
□ Diagonal branch
 
	
 
□ Circumflex.
 
□ Proximal □ Mid □ Distal
 
□ Obtuse Marginal
 

4. Type of stent with ISR	$: \square BMS \square DES Sirolimus \square DES$	Everolimus 🗆 DES Paclitaxel
	□ DES Zotarolimus □ DES other	drug Specify

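### Exclusion 14 and the device's Instructions for Use define different populations: a woman planning a pregnancy passes the eligibility checklist but falls under the IFU's prohibition

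*Combined protocol and SAP*

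**What the plan says.** Item 14 of the exclusion criteria in section 3.9 reads "Pregnant or lactating females". The protocol summary and the Exclusion Criteria Form in Appendix L carry the same words. The form states that a subject is eligible only if every exclusion item is answered no.

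The IFU is Appendix E. Its section 8.3, on carcinogenicity, genotoxicity and reproductive toxicology, states: "Do not use the CVT Everolimus-coated PTCA Catheter in women who are pregnant or intending to become pregnant". Its section 5.1, Contraindications, contains a single instruction: "Refer to the Clinical Investigational Plan for study exclusion criteria".

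One screening step bears on this. Section 4.1 says: "A pregnancy test should be administered to all female subjects of childbearing potential within 14 days prior to the procedure". The pre-procedure laboratory page of the CRF asks "Is the subject female and of childbearing potential" and then records the sample date and the test result.

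Two other provisions are relevant. Section 4.3 says that all catheters, the study device included, "should be delivered and deployed per their respective Instructions for Use". Exclusion 11 in section 3.9 applies where "Subject is not in the opinion of the investigator an acceptable candidate to participate in the study".

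**The concern.** The protocol and the device labelling bound into it should agree on who may be treated. Here a site that completes the eligibility form correctly can pass a woman whom the IFU rules out.

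The layout makes the gap easy to miss. The IFU's introduction directs operators to the indications, contraindications, restrictions, warnings and precautions. The wider prohibition is in none of these; it stands in a toxicology paragraph under Drug Information. A reader who goes to the contraindications section is sent to the protocol's exclusion list, which lacks the rule.

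The situation is one the plan foresees. It provides for women of childbearing potential in section 4.1 and on the CRF, and its definition of a serious adverse event in section 5.5 includes foetal outcomes. Section 9.6 calls this a first-in-human study. What is at stake is subject protection and a consistent eligibility rule, not the precision of any estimate.

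**Working it through.** No calculation applies; the check is a comparison of the texts.

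**Step 1: the population each text rules out.**

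| Woman at screening | Exclusion 14 (summary, 3.9, CRF) | IFU 8.3 |
|---|---|---|
| Pregnant | Excluded | Use prohibited |
| Lactating, not pregnant, no pregnancy planned | Excluded | Not mentioned |
| Not pregnant, not lactating, planning a pregnancy | Passes | Use prohibited |
| None of these | Passes | Not mentioned |

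The two rules agree on the first and last rows and differ on the middle two. The third row is the one that matters in practice, because the eligibility form lets her through. The second row is a mismatch in the opposite direction and does no harm at enrolment, since the protocol already excludes her. It does show that neither text contains the other.

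**Step 2: whether another screening step catches the woman in the third row.**

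- The pregnancy test, taken within 14 days before the procedure, detects a current pregnancy. It says nothing about plans.
- The CRF laboratory page records childbearing potential and the test result. It does not ask about intention.
- The other criteria in sections 3.8 and 3.9 and the other CRF forms contain no contraception requirement and no question about planned pregnancy.
- Exclusion 11 would let an investigator decline her, but it is discretionary, does not mention pregnancy and prompts no question.

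**Step 3: whether the IFU corrects this through its own list.** Section 5.1 defers to the protocol. Sections 5.2, 6 and 7 (restrictions, warnings, precautions) do not mention pregnancy. The cross-reference therefore leads back to the narrower list.

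**Step 4: how many subjects.** The documents give no figure. If 0 to 2 of the 50 subjects were affected, which is an assumption, the share would be 0/50 = 0% to 2/50 = 4%. Zero is plausible: the group is only those women of childbearing potential who also plan a pregnancy, within a coronary in-stent restenosis population.

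**The case against.** The strongest reply is that the documents have to be read together. The IFU is part of the protocol. Its cover requires all instructions, precautions and warnings to be read and understood before use, its introduction expects operators to know its contents, and section 9.3 requires completed device training. On that view the prohibition is already in front of the operator, and exclusion 11 gives the investigator the means to act on it. Part of this stands: the gap lies in the eligibility criteria and the CRF. A reader might infer that the protocol as a whole permits or endorses treating such a woman, and the documents do not support that. What remains is that the checklist passes her and no visible step asks the question.

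A reader might also infer that treating her would be a protocol deviation, because section 4.3 refers to the IFU. That is not established. The sentence concerns how catheters are delivered and deployed, in a paragraph about the procedure and the capture of inflations. Whether it reaches patient selection is open.

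Nor does the absence of long-term carcinogenicity studies, stated in IFU 8.3, strengthen the point. It applies to every subject, not particularly to women planning a pregnancy.

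Finally, Appendix C, the informed consent form, was not available for review and may contain wording on pregnancy or contraception. Such wording would not change item 14 or the CRF, but it could affect whether a site would treat such a woman unknowingly. The IFU and CRF copies are also marked as possibly not the most current versions.

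**Conclusion.** The inconsistency is real. Exclusion 14 and IFU 8.3 describe different populations, and IFU 5.1 refers the reader to the narrower one. A woman who is neither pregnant nor lactating and who plans a pregnancy is eligible on the checklist and barred by the IFU.

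The practical size is small: few subjects, possibly none, and a negligible effect on freedom from target lesion failure and on late lumen loss. The point still merits correction because it concerns subject protection and is cheap to settle.

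The textual mismatch rests on no assumption beyond the copies supplied being those in use. The number affected is an assumption. The statement that nothing asks about intention is limited to the pages available, which exclude the consent form. The documents do not show which of the two rules the sponsor intends.

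**What to change.** Reconcile item 14 in the protocol summary, in section 3.9 and on the Exclusion Criteria Form in Appendix L with sections 5.1 and 8.3 of the IFU, so that protocol, CRF and IFU state one population. The reconciliation should cover lactation as well, since IFU 8.3 does not mention it. Which rule is right is for the sponsor to confirm.

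Then align the CRF screening question with the confirmed rule. If that rule refers to intention, note that IFU 8.3 gives no period over which intention is judged, so a yes/no item would need one stated to be answered consistently across sites. The consent form should be checked for agreement at the same time.

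The cost is a short edit to the protocol, the CRF and, depending on the outcome, the IFU. The only downside is the possible loss of an occasional candidate if the wider rule is kept.
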